Extensive research has examined the role that neuroactive steroids play in alcohol's effects (Morrow et al., 1999; Morrow et al., 2001). For example, acute alcohol increases levels of neuroactive steroids in plasma (VanDoren et al., 2000) and brain (Sanna et al., 2004), and blockade of neuroactive steroid production by the 5 α -reductase (5 α -R) inhibitor finasteride attenuated acquisition of alcohol preference in mice (Ford et al., 2008). In humans, the plasma concentration of ALLO was increased following severe intoxication (Torres and Ortega, 2003, 2004), but not moderate intoxication (Holdstock et al., 2006; Nyberg et al., 2005; Pierucci-Lagha et al., 2006). Importantly, chronic alcohol exposure reduces both plasma and brain levels of ALLO (Morrow et al., 2001). Clinical studies have also shown that variation in genes that encode neuroactive steroid synthesis enzymes was associated with alcohol dependence (Milivojevic et al., 2011) and subjective effects of alcohol (Milivojevic et al., 2014), which may modulate risk for the development of dependence. Moreover, nicotine has been found to increase neuroactive steroids (Porcu et al., 2003). Unlike alcohol dependence, their levels were found to be higher in smokers, in whom levels of ALLO positively correlated with nicotine dependence severity (Marx et al., 2006).

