3. **Research Plan:** Summarize the study design and research procedures using non-technical language that can be readily understood by someone outside the discipline. **Be sure to distinguish between standard of care vs. research procedures when applicable, and include any flowcharts of visits specifying their individual times and lengths.** Describe the setting in which the research will take place.

1. Study Design and Overview

Ninety treatment seeking men and women with AUD will be recruited to participate in and complete this preliminary study. Participants will be recruited through flyers and advertisements in local newspapers and from community substance abuse treatment facilities. Subjects will participate in an initial screening and intake session to obtain informed consent, followed by physical examination and blood work to determine eligibility. Eligible

participants will be randomly assigned to 2 doses of PREG (300/500 mg/day) vs placebo (PLA) treatment (N=30/group) over 8 weeks. In week 2, AUD patients will participate in a 3day human laboratory study where they will be exposed to three experimental sessions of stress, alcohol cue and neutral-relaxing imagery on separate days (Fox et al.,2007; 2009; Sinha et al., 2008; 2009; 2011). Throughout the study, participants will come twice-weekly to the Yale Stress Center to receive medication, counseling and provide urine samples for UTOX. Women will be enrolled during the mid-luteal phase of the menstrual cycle so that laboratory sessions will be scheduled during the early to mid-follicular phase of the cycle when endogenous sex hormone levels are low prior to ovulation. PREG doses and matching placebo will be obtained by Yale IDS for compounding and dosing to 300mg and 500mg of PREG or PLA. Participants will self-administer study medication on a twice-daily dosing schedule throughout entire study.

Subjects will begin with full respective dose of medication immediately without a titration period, as previous studies with similar doses of pregnenolone up to 500 mg/day at b.i.d. dosing to be well tolerated and with no side effects (Marx et. al., 2009; Marx et al., 2014; Brown et al., 2014; Sripada et al., 2013).

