Laboratory Sessions. In week 2 of the study PREG/PLA administration and hence DAY 1, 2 and 3 of the laboratory portion of the study, subjects will be brought into the research testing rooms of the Yale Stress Center (YSC) at 2:00 PM. The laboratory sessions will only be conducted if the subject has a breath alcohol level of 0, otherwise the session will be rescheduled. The subject will then be prepared for physiological assessments. An indwelling intravenous (IV) catheter will be inserted by the research nurse specialist in the antecubital region of the subject's non-preferred arm for blood sampling. Blood samples will be obtained periodically for assessment of neuroactive steroids, ACTH, cortisol, prolactin, NE and EPI levels. A blood pressure cuff will be placed on the subject's preferred arm to monitor blood pressure (BP) periodically. On-line assessment of physiological measures will be obtained at specified time periods during the laboratory sessions. Self-reports of emotional state, anxiety and alcohol craving will also be assessed periodically.

After preparation of assessments and a 40 minute adaptation period, two blood draws before imagery will be conducted (BASELINE). After the second blood draw, a 5-minute baseline period will follow to assess continuous pulse rate and BP assessments. Following the baseline period, instructions for conducting imagery will be provided. The order and content of the imagery condition will not be revealed to the subject or to the research staff conducting the

sessions. In the imagery task the subjects will be asked to imagine the situation being described vividly, 'as if it were happening right now", until asked to stop. The imagery script will be played to the subject over headphones and the subject will be required to imagine the situation for 5 minutes. A tape recording for each subject's script will be developed prior to the testing situation and recorded by the same person for each subject. Immediately following imagery, a blood draw will be conducted (IMAGERY). Thereafter, four recovery blood draws will be conducted at 15 minute intervals (RECOVERY). Timeline for assessments is detailed in Table 1.

TABLE 1: Schedule for Laboratory Sessions

LAB DAY 1 11AM: Imagery and Relaxation Training and IV Habituation session (1 hour)

LAB DAY 1, 2 and 3: LABORATORY (IMAGERY) TESTING SESSIONS

2:00 PM	Set-up for plasma (IV insert) measures; physiological Setup - HR, BP, Finger Temp, SCL.

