For both HPA and catecholamine assays, data will be analyzed for the time-points outlined in Table 1. In addition, as each measure may show different response profiles over time, we will also assess maximal or peak response and area under the curve (AUC) for each measure. Peak and AUC assessments of these measures are commonly used methods to reduce variability in responses and have been used in several studies (Kirschbaum, Wust, Faig, & Hellhammer, 1992; O'Malley, Krishnan-Sarin et al. 2002).

d. Neuroactive Steroid Measures. To assess plasma levels of pregnenolone, allopregnanolone and androstanediol, a 1mL of plasma will be collected at each timepoint, and processed as per above. Analysis of these neuroactive steroids will be conducted at The Chemical Instrumentation Center at Yale, which has a state of the art gas chromatography/ mass spectrometry (GC/MS) instrumentation (Agilent 5973 GC-MS w/autosampler, HP 5971A GC-MS) following procedures outlined in Milivojevic et al., 2016).

Assessments: A trained research assistant will meet with the client at various time-points to assess the client on selected substance use and psychological functioning measures using structured interviews, self-report assessments and to obtain urine samples (at the Yale Stress Center) for toxicology screens. A description of the assessment battery follows.

Screening Assessments:

Assessment of IQ and Executive Functioning. *The Shipley Institute of Living Scale (Shipley 1940)* is a paper and pencil test taking about 15-20 minutes to complete. It consists of two parts (vocabulary and abstraction) which when combined provides a global measure of cognitive functioning and IQ. The Shipley will be administered to ensure that subjects will be able to successfully participate in the self-report components and comprehend all aspects of the protocol.

Sociodemographic/general patient information. Demographic data, medical history, and family psychiatric history will be assessed with interviews and self-report forms that provide data on age, race, socioeconomic status, marital status, psychiatric family history, educational and occupational levels, and significant medical history.

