During each laboratory session, about 120mL of whole blood will be drawn to measure stress hormone levels that may change during the session, totaling 360 mL for all three laboratory sessions. The amount of blood drawn over three laboratory sessions is equal to a little over onehalf the blood obtained during a regular blood donation. In addition, 32 mL of whole blood will be drawn on the first day of laboratory session to look at genetic markers, and 10mL of whole blood will be drawn during the physical exam/admission procedure to assess eligibility and look at molecular adaptations during the study. Lastly, 15 mL of whole blood will also be drawn each at weeks 2, 5 and 7 to measure pregnenolone levels. These levels will allow staff to ensure subjects are taking medication as prescribed. Thus, a total amount of 432 mL of whole blood will be drawn throughout the entire study. People who are in good health are not usually affected by this kind of blood loss. However, to be safe, subjects will be warned against donating blood for at least eight weeks after completing this study and 5 weeks beforehand.

III) Laboratory Sessions:

(1). Intravenous (IV) Catheter: When an IV is started, there is some risk that subjects may develop a bruise or bleeding where the vein is punctured. If this occurs, appropriate treatment will be instituted immediately. On extremely rare occasions, fainting, blood clot or infection may occur.

(2). The Imagery Procedures: The imagery method involves reliving a personal stressful event and can be somewhat anxiety provoking at the time of the task. Our previous experience has shown that once the task is over, there is very little anxiety that carries over, thus posing minimal risk. The alcohol cue imagery involves reliving a personal experience involving alcohol-related stimuli associated with alcohol use. While subjects may feel aroused by the alcohol cue imagery, relaxation procedures have been shown to be successful in reducing the physiological arousal associated with cue exposure and stressful imagery. It is likely that moderate craving for alcohol may occur due to subjects' imagining and reliving stressful events and drug cue related events. It is also possible that craving for alcohol may linger even after the task. In order to ensure that subjects are not put at increased risk for alcohol consumption after the laboratory sessions, the following safeguards will be taken:

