Hypothesis 3a: AUD patients on PREG doses versus those on PLA will dose dependently show (a) Primary: higher alcohol abstinence days, lower mean heavy drinking days and lower amounts of alcohol used in the 8-week treatment period, and (b) secondary: lower alcohol craving, anxiety and negative mood symptoms.

Specific Aim #3b: To assess whether PREG-stimulated ALLO levels mediate its effects on primary alcohol use outcomes and on secondary clinical outcomes during the 8-week treatment phase. Hypothesis 3b: Compared to PLA, higher ALLO levels in the PREG dose groups will dose dependently mediate primary and secondary alcohol use outcomes predicted in the above Hypothesis 3a with the PREG 500mg group showing better primary and secondary outcomes than the PREG 300mg group who will be better than outcomes in the PLA group.

Exploratory Aim: To explore whether pre-treatment patient characteristics (gender, family history of alcoholism (FH), trauma history and co-morbid drug use) influence PREGpotentiated ALLO levels and primary and secondary alcohol use outcomes.

Exploratory analyses using mixed effects models and MRMs will be conducted to assess if pretreatment characteristics and laboratory responses (average or AUC) are predictive of primary alcohol use outcomes.

SECTION VI: RESEARCH INVOLVING DRUGS, BIOLOGICS, RADIOTRACERS, PLACEBOS AND DEVICES

If this section (or one of its parts, A or B) is not applicable, state N/A and delete the rest of the section.

A. DRUGS, BIOLOGICS and RADIOTRACERS

1. Identification of Drug, Biologic or Radiotracer: What is (are) the **name(s)** of the drug(s) biologic(s) or radiotracer(s) being used? Identify whether FDA approval has been granted and for what indication(s).

Pregnenolone is a naturally occurring steroid, which is available as a dietary supplement in health stores. **Under the Dietary Supplement Health and Education Act of 1994 (DSHEA), a dietary supplement is not considered a drug if the intended use is only to affect any function of the body.** In this pilot study, we are looking at pregnenolone's effect on function in the body and we will be collecting preliminary alcohol and drug use outcome data.

All protocols which utilize a drug, biologic or radiotracer **not** approved by, but regulated by, the FDA, or a radiotracer regulated by the RDRC, must provide the following information:

- a. What is the Investigational New Drug (IND) **number** assigned by the FDA?
- b. Who holds the IND?

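### Aim 3b leaves the ALLO-to-drinking path confounded by each patient's usual drinking level, so mediation can be found when ALLO has no effect on drinking

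*Combined protocol and SAP*

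**What the plan says.** Section V.12, Hypothesis 3b, predicts that "higher ALLO levels in the PREG dose groups will dose dependently mediate primary and secondary alcohol use outcomes". It takes its outcomes from Hypothesis 3a: abstinent days, heavy drinking days and "lower amounts of alcohol used in the 8-week treatment period". It names no ALLO time point, no lag and no mediation model.

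ALLO sampling appears under the laboratory component of Section V.3. Under Laboratory Sessions: "Blood samples will be obtained periodically for assessment of neuroactive steroids, ACTH, cortisol, prolactin, NE and EPI levels". Under Neuroactive Steroid Measures: "To assess plasma levels of pregnenolone, allopregnanolone and androstanediol, a 1mL of plasma will be collected at each timepoint". The Study Design and Overview dates these sessions: "In week 2, AUD patients will participate in a 3day human laboratory study". For the treatment phase, Section V.9 (Drawing of Blood) says that "15 mL of whole blood will also be drawn each at weeks 2, 5 and 7 to measure pregnenolone levels", and Section VI.A.3 describes those draws as a compliance check. No pre-treatment ALLO assay is described.

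The Background (Section V.2) states that "chronic alcohol exposure reduces both plasma and brain levels of ALLO". Under Data Analytic Procedures (Section V.12), a baseline variable becomes a covariate only if the treatment groups are found to differ on it.

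**The concern.** A mediation claim needs two paths: drug to ALLO, and ALLO to drinking. Randomisation protects the first. It does nothing for the second, which compares patients within an arm who happen to have higher or lower ALLO. If drinking lowers ALLO, as the protocol says, a patient with a stable high drinking level tends to have a low week-2 ALLO and a high 8-week total. The ALLO-to-drinking coefficient is then negative even if ALLO does nothing. A second, smaller contribution comes from drinking in weeks 1-2, which precedes or coincides with the sample yet counts in the outcome.

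The covariate rule does not catch this. It looks for imbalance between arms, whereas the confounding operates within arms and is present when the arms are perfectly balanced. The mechanism is a specific aim of the trial, and the findings are meant to guide a larger one, so a false mechanism would carry forward.

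**Working it through.** **Inputs from the documents.** Three arms of 30 (90 in total); an outcome window of 8 weeks (56 days); ALLO sampled in week 2. The plan gives no alpha, effect size, SD or drinking-ALLO correlation, and no figure for this test, so there is nothing to reproduce.

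**Assumptions.** ALLO has no effect on drinking. The drug shifts ALLO by +1.0 SD (300 mg) and +1.5 SD (500 mg). The within-arm correlation r between weeks 1-2 drinking and week-2 ALLO is 0 to -0.3. Each week's drinking is a stable personal level plus independent weekly variation, with week-to-week correlation ρ of 0.4 or 0.6. The 90-day baseline is treated as a 12-week mean. Mediation is declared when 500 mg versus placebo on ALLO, and ALLO on drinking given arm (negative sign), are both significant at two-sided 0.05. The nominal rate in the claimed direction is therefore 2.5%.

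**Step 1: overlap.** Between 7/56 = 12.5% and 14/56 = 25% of the outcome window falls before or during the sampling week.

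**Step 2: how much of r reaches the outcome.** The mean of k weeks has variance ρ + (1-ρ)/k.
- Weeks 1-2 with weeks 1-8: √{[ρ+(1-ρ)/8] / [ρ+(1-ρ)/2]}. This is √(0.475/0.70) = 0.82 at ρ = 0.4 and √(0.65/0.80) = 0.90 at ρ = 0.6.
- Weeks 1-2 with weeks 3-8: ρ / √{[ρ+(1-ρ)/2] × [ρ+(1-ρ)/6]}. This is 0.4/√(0.70×0.50) = 0.68 and 0.6/√(0.80×0.667) = 0.82.

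At r = -0.2, the spurious ALLO-drinking correlation is about -0.16 to -0.18 for the full 8 weeks and still about -0.14 to -0.16 for weeks 3-8. Removing the overlap alone changes little.

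**Step 3: chance that it is significant.** With 90 - 4 = 86 df, the critical t is 1.99 and the noncentrality is c√86/√(1-c²). For r = -0.2, c = 0.165 gives 1.55 and a chance of about Φ(1.55 - 1.99) = 33%; c = 0.180 gives 1.70 and about 39%. With the assumed shifts the drug-to-ALLO path is almost always significant, so these are close to the false-mediation rates.

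**Step 4: simulation.** 4,000 trials per setting. Ranges (%) run over both values of ρ and a drug effect on drinking of 0 or -0.5 SD at 500 mg (half that at 300 mg).

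| Outcome and adjustment (arm always included) | r = 0 | r = -0.1 | r = -0.2 | r = -0.3 |
|---|---|---|---|---|
| Weeks 1-8, arm only | 2.2-2.5 | 11-14 | 33-40 | 64-73 |
| Weeks 1-8, plus baseline drinking | 2.4-2.6 | 4-6 | 9-12 | 14-23 |
| Weeks 3-8, arm only | 2.2-2.6 | 8-12 | 24-35 | 47-65 |
| Weeks 3-8, plus baseline drinking | 2.2-2.7 | 3 | 4-5 | 5-6 |
| Weeks 3-8, plus baseline and weeks 1-2 drinking | 2.1-2.9 | 2.4-2.5 | 2.4-2.8 | 2.4-2.8 |

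A separate simulation of the first row gave 12-13%, 34-39% and 66-73%; these are the figures quoted in the conclusion.

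**Step 5: price of the fullest adjustment.** When ALLO truly has a constant effect on drinking, adding weeks 1-2 drinking to the model shrinks the estimated ALLO path by about 13%.

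**The case against.** **The analysis is inferred.** A reader might infer that the plan prescribes regressing an 8-week drinking total on week-2 ALLO. It does not: the 8-week window is explicit, but the ALLO time point follows only from the sampling schedule, and mixed models leave room for repeated outcomes. This stands as a limit on wording. It does not remove the problem, because week 2 is the only ALLO sampling described and no default drinking adjustment is stated.

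**Weeks 5 and 7.** A reader might infer that these samples are for pregnenolone alone. The text names pregnenolone but never says only, and the steroid assay described in Section V.3 covers ALLO as well. Aim 3b also speaks of the 8-week treatment phase, so later ALLO values may be intended. The documents leave this open.

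**The cause.** A reader might blame the overlap of weeks 1-2 with the sample. At r = -0.2, dropping those weeks alone still leaves 24-35%, whereas keeping them and adjusting for baseline drinking leaves 9-12%. Stable drinking level is the main driver.

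**Sign and size of the reverse path.** The Background also reports that acute alcohol raises neuroactive steroids, in humans after severe but not moderate intoxication. Sessions require a zero breath alcohol reading, which limits acute effects but not those of drinking on earlier days. Still, the net correlation during the first two weeks of dosing is undocumented.

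**Status of the trial.** Section V.12 calls the study preliminary and mostly descriptive and sets no rule for declaring mediation. That tempers the consequence. The same section nevertheless says mixed models will test the hypotheses of each aim.

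**Conclusion.** The concern holds in this form: the ALLO-to-drinking path in Aim 3b is confounded by stable drinking level and, to a lesser degree, by drinking in weeks 1-2, and the plan contains nothing that reliably removes either. With no true ALLO effect, false mediation in the claimed direction is about 12-13%, 34-39% or 66-73% at assumed correlations of -0.1, -0.2 or -0.3, against a nominal 2.5%.

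These rates rest on the assumed correlations, a week-to-week drinking correlation of 0.4-0.6 and a strong drug effect on ALLO. A weaker effect on ALLO would lower them, because the first path would fail more often. At a correlation of zero there is no inflation.

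A reader might instead quote 15%, 46% and 82%. Those are the power to detect correlations of 0.1, 0.2 and 0.3 between ALLO and the whole outcome; they do not model early drinking and overstate the size here. The documents support saying that the planned analysis can produce false mediation, not that it will.

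**What to change.** For Aim 3b, amend Section V.12 as follows:
- Name pre-imagery week-2 ALLO as the mediator, state how the values from the three sessions are combined, and state the mediation model.
- Use drinking in weeks 3-8 as the outcome. Always adjust for 90-day baseline drinking from the Substance Use Calendar, whatever the comparison of arms shows (false mediation about 3-6%).
- Add a second model that also adjusts for weeks 1-2 drinking (about 2-3%) and report both. Full dosing starts at once, so ALLO may already act in those weeks, and the second model then removes part of a true effect (about 13% in simulation).
- State whether the week 5 and 7 samples will be read for ALLO. If so, relate each value only to drinking after that sample.

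The drinking data are already collected daily for the 90 days before treatment and throughout it, so the main change is wording. An ALLO read-out at weeks 5 and 7 would use blood already drawn. Its feasibility needs checking, because Section V.3 allows specimens to be given at an outside laboratory and does not describe plasma handling for those draws. The statistical cost is that weeks 1-2 drinking leaves the mediation outcome, with slight attenuation in the second model. Hypothesis 3a is unchanged.

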Specific Aim 2b: To assess whether PREG-stimulated ALLO levels mediate its effects on provoked craving, HPA dysregulation, anxiety, mood and cognitive flexibility in the laboratory component.

Specific Aim 3a: To assess the preliminary efficacy of 8-week PREG 300 and 500 doses vs. PLA treatment on primary alcohol use outcomes and secondary outcomes of alcohol craving, anxiety and mood.

Specific Aim3b: To assess whether PREG-stimulated ALLO levels mediate its effects on primary alcohol use outcomes and on secondary clinical outcomes during the 8-week treatment phase.

Exploratory Aim: To explore whether pre-treatment patient characteristics (gender, family history of alcoholism (FH), trauma history and co-morbid drug use) influence PREG-potentiated ALLO levels and primary and secondary alcohol use outcomes.

2. Background: Describe the background information that led to the plan for this project. Provide references to support the expectation of obtaining useful scientific data.

Evidence from clinical surveys indicates that stress frequently leads to continued drug use and relapse (Marlatt and Gordon 1985; Bradley, Phillips et al. 1989; Wallace, 1989; Hodgins, el Guebaly, & Armstrong, 1995; Miller & Tonigan, 1996). Animal studies have shown that acute behavioral stress facilitates drug self-administration and reinstatement to drug seeking behavior in drug-addicted animals that have been drug-free for extended time periods (Shaham et al., 1995). Previous work in our laboratory has shown that exposure to previous stressful experiences consistently increases drug craving and stress-related arousal in alcohol and alcohol dependent individuals (Sinha et al., 1999a; 2000; 2003a). Data also suggests that stress-induced alcohol craving and related HPA and autonomic arousal are predictive of alcohol relapse after inpatient treatment (Daughters et al., 2009; Fox et al., 2009; Sinha et al., 2003). These data suggest that attenuation of stress-induced alcohol craving, and their related arousal, may be a useful target in drug relapse prevention.

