Reporting of Other Study-Safety Events: The project PI will inform the Data Safety Monitor, the Yale HIC, NIDA project officer and the sponsor promptly of any change in recruitment or other changes in this project that are relevant to safety, as well as any action taken by the Yale HIC as a result of continuing review of this project.

12. Statistical Considerations: Describe the statistical analyses that support the study design. For this preliminary study data we will mostly use descriptive statistics for comparing the medication groups on primary outcome measures and safety measures. Repeated measures ANOVA and mixed model procedures to assess treatment group differences in alcohol craving and stress related arousal (heart rate, blood pressure, HPA and catecholamine responses) during laboratory exposure to stress and drug cues as compared to neutral imagery conditions. Non-parametric tests will be used to assess occurrence of side effects, alcohol use measures, CIWA scores and perceived stress scores during the treatment study phase. The number and type of AE's for the two medication groups will be conducted using t-tests, chisquare tests and ANOVAs as appropriate. Findings will be used to estimate effect sizes for the medication and guide the larger randomized clinical trial in the future.

Primary Outcome Measures during 8 week treatment: The primary outcome measures will be:(1) alcohol use as measured by weekly urine drug screens and self-report of drug use on the Substance Use Calendar, (2) side effects and adverse events as measured by the SAFTEE, and (3) treatment adherence as measured by frequency of attendance for medication selfadministration and attendance for counseling appointments, including missed sessions.

Secondary Outcome Measures: Secondary outcome measures will include alcohol craving scales, alcohol withdrawal assessment using the CIWA, perceived stress scale, the recent stressful life events scale (LES), and the COPE Questionnaire. In addition, other assessments will be used to ensure that medications groups are not different in various measures at baseline and also to assess their role in predicting treatment response. Examples of such

assessments would be demographic measures, depressive and anxiety symptoms, motivation to change and thoughts about abstinence, which are measures that have been found to predict substance abuse treatment outcomes (Hall et al., 1990; 1991; McMahon et al., 1986).

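### The Exploratory Aim poses an effect-modification question, but the only analysis stated for it is a prediction analysis with no treatment-by-characteristic term

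*Combined protocol and SAP*

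**What the plan says.** Section V.1 (Statement of Purpose) states the aim as "To explore whether pre-treatment patient characteristics (gender, family history of alcoholism (FH), trauma history and co-morbid drug use) influence PREG-potentiated ALLO levels", together with the primary and secondary alcohol use outcomes. Section V.12 (Statistical Considerations) repeats it; there the characteristics are to "influence PREGpotentiated ALLO levels and primary and secondary alcohol use outcomes".

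The analysis that follows in Section V.12 is a single sentence. It begins "Exploratory analyses using mixed effects models and MRMs will be conducted" and gives the purpose as to "assess if pretreatment characteristics and laboratory responses (average or AUC) are predictive of primary alcohol use outcomes". The model terms are not listed.

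Three other places bear on the point:

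- **Data Analytic Procedures (Section V.12).** The laboratory component crosses treatment arm with sex as between-subject factors. The fixed effects then listed for the mixed models are sex, imagery condition and time period. Neither treatment nor any interaction is in that list.
- **Study Design and Overview (Section V.3).** The laboratory sessions take place in week 2, after randomisation and on study medication.
- **Secondary Outcome Measures (Section V.12).** Other baseline assessments will be used "also to assess their role in predicting treatment response".

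**The concern.** Pregnenolone-potentiated ALLO exists only as a drug effect, that is, as a difference from what ALLO would have been without the drug. Asking whether a characteristic influences it is asking whether the drug effect differs by that characteristic. For alcohol outcomes the aim's wording is looser, but the same reading is plausible.

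The stated analysis asks something else: whether the characteristic goes with the outcome. A factor that marks heavier drinking equally in all three arms passes that test. A factor that changes the drug's effect can fail it. The ALLO and secondary-outcome limbs have no analysis at all.

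The laboratory responses add a further difficulty. Hypothesis 2a expects the drug to change them, so they are post-randomisation variables and cannot stand on the same footing as baseline characteristics.

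The plan says its findings will be used to estimate effect sizes and to guide a larger trial. If a prognostic marker were taken for a marker of drug response, that guidance would be wrong.

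**Working it through.** **No figure to reproduce.** The documents give no alpha, power, effect size or SD for this aim. From the documents: three arms of 30, 90 in total; four named characteristics; three primary drinking measures in Hypothesis 3a; women half the sample. Assumptions: two-sided alpha 0.05, outcome SD 1, a binary characteristic Z split 50/50 within each arm, no dropout. The effect sizes are illustrative.

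**1. What the predictor-only coefficient measures.** Write the outcome as

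Y = b0 + b1·T300 + b2·T500 + b3·Z + b4·T300·Z + b5·T500·Z + error.

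Here b3 is the association on placebo (prognosis), and b4 and b5 are the differences in drug effect by Z (modification). Regressing Y on Z alone, with equal allocation, estimates b3 + (b4 + b5)/3. One number mixes the two quantities, and no sample size separates them.

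**2. Purely prognostic factor (b4 = b5 = 0).** The comparison is 45 against 45, so the variance is 2/45 = 0.0444 and the SE 0.211. Power ≈ Φ(d/0.211 − 1.96). The simulation used 10,000 trials per setting with no treatment effect.

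| Prognostic effect d | Predictor-only, formula | Predictor-only, simulated | Interaction (2-df F), simulated |
|---|---|---|---|
| 0.3 SD | 0.296 | 0.296 | 0.050 |
| 0.5 SD | 0.660 | 0.656 | 0.052 |
| 0.8 SD | 0.967 | 0.962 | 0.053 |

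Adding a 0.5 SD drug effect changes the predictor-only figures little (0.276, 0.626, 0.957), and the interaction test stays at 0.049–0.050.

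For a continuous characteristic correlating 0.2, 0.3 or 0.4 with the outcome, a 6,000-trial simulation gave 47%, 82% and 98%, with the interaction test at 4.5–5.1%. The approximation Φ(√87·atanh(r) − 1.96) agrees: 0.47, 0.82, 0.98.

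**3. True modifier with no average effect.** Take b4 = b5 = 0.8 and b3 = −0.8 × 2/3 = −0.533. The predictor-only coefficient is then −0.533 + 1.6/3 = 0. Simulated rejection is 4.4% for the predictor-only test and 33% for the interaction test.

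**4. What the interaction can deliver with 90 participants.**

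- Both doses pooled against placebo: variance 1/30 + 1/30 + 1/15 + 1/15 = 0.200, SE 0.447. This is 0.200/0.0444 = 4.5 times the main-effect variance.
- One dose against placebo: variance 4/15 = 0.267, SE 0.516.
- Power at 0.5 SD: Φ(0.5/0.447 − 1.96) = 0.20 pooled; Φ(0.5/0.516 − 1.96) = 0.16 for one dose.
- Detectable with 80% power: (1.96 + 0.842) × SE = 1.25 SD pooled, 1.45 SD for one dose.
- 95% confidence interval half-width: 1.96 × SE = 0.88 SD pooled, 1.01 SD for one dose.

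**5. Multiplicity.** Four unadjusted independent tests give 1 − 0.95⁴ = 18.5% family-wise error. Four characteristics by three drinking outcomes give 1 − 0.95¹² = 46%.

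**The case against.** The strongest reply is that the plan does what it says. The wording on alcohol outcomes can be read as prognostic, and a prediction analysis answers a prognostic question. On that reading, the rejection rates in step 2 are power for a true association, not false positives. This stands for the alcohol limb, but it cannot rescue the ALLO limb.

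Model terms are unspecified, so an interaction is omitted, not ruled out. That also stands. The difficulty is that the one purpose stated for the models is prediction.

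Sex is partly covered. Crossing treatment with sex implies that interaction for the laboratory outcomes. It does not reach the 8-week drinking outcomes or the other three characteristics.

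The phrase "assess their role in predicting treatment response" may look like proof that modification was intended. In context it concerns other baseline measures, such as demographics, mood and motivation, which the plan describes as known predictors of treatment outcome. That is a prognostic sense, so the phrase settles nothing.

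A reader might also infer that ALLO potentiation cannot be studied because no pre-dose ALLO is scheduled, especially since Section V.2 (Background) notes that "chronic alcohol exposure reduces both plasma and brain levels of ALLO". This does not follow. Within each level of a characteristic, the randomised placebo group supplies the reference. Differences in ALLO between levels that predate dosing cancel in expectation from the interaction contrast.

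Finally, the interaction is poorly powered here and the study is preliminary. Both are true. They argue for estimates with intervals, and do not make a prediction analysis answer a modification question.

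**Conclusion.** The concern holds as a mismatch between question and method. The stated analysis cannot tell prognostic factors from modifiers, and the ALLO and secondary-outcome limbs have no analysis. Under the assumptions in the working, the predictor-only test would misinform about modification in both directions: a purely prognostic factor is significant in about 30–98% of trials across the strengths examined, and a genuine 0.8 SD modifier with no average effect in 4.4%. The formula in step 1 needs only equal allocation; the percentages depend on assumed effect sizes.

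It would go too far to say that the trial will report prognostic factors as modifiers. The plan's own word is predictive, and it says nothing about selecting patients for the larger trial by these characteristics. The risk is that a reader or a later trial team draws that conclusion. Because the aim is exploratory in a preliminary study of 90, this is something that should be corrected, not a threat to the main results.

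**What to change.** Replace the exploratory-analysis sentence in Section V.12 with text to this effect:

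- For each of the four named characteristics, fit treatment, the characteristic and characteristic × treatment, with placebo as reference. Do this for on-treatment ALLO and for each primary and secondary alcohol outcome.
- Report each interaction as an estimate with a 95% confidence interval, labelled hypothesis-generating, and state how many were examined.
- Report main effects of characteristics as prognostic only.
- Analyse week-2 laboratory responses separately, as post-randomisation predictors.

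The cost is a few sentences, with no new visits, participants or assays. A pre-dose ALLO assay is not needed. Nor do the documents establish that plasma is available: the blood taken at the physical examination is assigned to eligibility and molecular (RNA) work.

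The downside is low precision, with interaction intervals of roughly ±0.9 to ±1.0 SD under the assumptions above. Most results will be inconclusive, and the text should say so in advance.
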